(LMP: last menstrual period; GA: gestational age; ICD: informed consent document; MUAC: mid-upper arm circumference; Hb: haemoglobin; RDT: rapid diagnostic test (for malaria); HH: household; SES: socioeconomic status; KAP: knowledge, attitude and practice; ANC: antenatal care; WASH: water, sanitation and hygiene; MN: micronutrients; HC: head circumference; IYCF: infant and young child feeding)

The detailed procedures of study 1 are summarized in Table 3 below.

Table 3: Study 1 summary table of procedures and assessments

Study Periods	Screening		Intervention Period			
Visit/Round	0	1	2	3	4	5
Time (hour, day, week)	≤20 wk GA	≤20 wk GA	34±1wk GA	Delivery +48h	Infant 6.5±1 mo old	Infant 24±1 mo old
Randomisation of clusters (done prior to recruitment)						
Oral consent for screening questions	x					
Pregnancy and health status questions	x					
In- /exclusion criteria	x					
Written participant information and informed consent		x				
Pregnancy test		x				
Re-assessment of in- /exclusion criteria		x				
Household demographics/characteristics		x				
Maternal education		x				
Maternal anthropometry		x	x	x	x	
Child anthropometry				x	x	x
Capillary blood sampling in women		x	x		x	
Capillary blood sampling in children				x	x	x
Ante-/postnatal care		x	x	x	x	
Dietary and nutrition practices KAP, dietary diversity (pregnancy, lactation)		x	x		x	
WASH practices		x	x		x	x
Delivery information (incl. breastfeeding, birth weight and length)				x		
Breastfeeding and other IYCF indicators					x	x
Child dietary diversity					x	x
Child morbidity					x	x
Intervention adherence			x	x	x	x

Study 2:

General study design: Study 2 is a cluster-randomized, parallel-group, prospective, follow-up effectiveness study over a period of 2 years comparing 2 groups of children 6-35 months of age at recruitment:

- a) Intervention group: All selected households with children 6-35 months of age at recruitment will receive MNP (1 sachet every three days per child) and ORS along with zinc (20 mg/day) for treatment of acute diarrhoea. The households will also be provided with soap, chlorine solution, poultry (8 chickens at start of intervention), and seeds for red onion and indigenous greens (March 2018 and March 2019). The products will be accompanied by monthly nutrition and WASH trainings. The products and trainings will be provided free of charge. Additionally, all households will receive the agricultural package as in the control group.

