- b) Control group: All households will be provided with agricultural training (every 2 weeks on

average) for free. In addition, households can also enrol for the following products on credit: compost booster, cook stoves, seeds (onions, maize, indigenous greens, beans), maize storage bags, drying tarps, trees, solar lights, fertilizer, actellic dust (insecticide), re-usable sanitary pads.

We anticipate recruiting 2,000 (1,000 in each group) children 6-35 months of age into the study (see section 7.2 for sample size calculation). Children will be recruited from 100 clusters (randomly assigned to intervention or control) that will be drawn from Lugari district in Kakamega County located in the Western Province of Kenya.

Questionnaire based and anthropometric data will be collected in **3 rounds** at a central place in walking distance from participant's homes one year apart from each other (Table 4). The following information will be collected in **round 1** (baseline assessment prior to the actual start of intervention distribution):

- Age
- Height and weight
- Household demographics/characteristics and caregiver's education
- Dietary diversity, breastfeeding and infant and young children feeding (IYCF) practices
- WASH practices
- Child morbidity

In **rounds 2 and 3**, information on dietary diversity, breastfeeding and IYCF practices, WASH practices and child morbidity will be collected again. Additionally, changes in adherence and coverage of the intervention package as well as unintended outcomes (e.g. reduction of exclusive breastfeeding due to premature introduction of complementary foods) will be assessed.

Table 4: Study 2 summary table of procedures and assessments

Study Periods	Intervention Period		
	1	2	3
Visit/Round	1	2	3
Time (hour, day, week)	Prior to start of intervention	1 year after start of intervention	2 years after start of intervention
Age (Date of birth)	x		
Anthropometry	x	x	x
Household demographics/characteristics	x		
Mother's/caregiver's education	x		
Dietary diversity, breastfeeding and child feeding practices	x	x	x
WASH practices	x	x	x
Child morbidity	x	x	x
Adherence to and coverage of intervention package		x	x

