As these are cluster-randomized studies, no individual randomization will take place. Clusters will be created according to village size and location with the aim to create clusters that correspond with village(s) boundaries and are big enough to likely have 10 pregnant women to be recruited in study 1, and 20 children in study 2. The clusters will be comprised of villages that are geographically close to one another and separate from other clusters. Once the clusters are determined, they will be randomly assigned to control or treatment in both studies.

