7.3.2 Recruitment and screening

Study 1:

During community meetings and outreach CHVs will inform and 1AF field officers will screen potential participants. In case a woman declares to be pregnant, oral consent for a screening assessment including providing the date of last menstrual period and checking for inclusion/exclusion criteria will be taken. If woman is eligible written informed consent will be sought and the woman will be asked to provide a urine sample for a pregnancy test. Women will be enrolled in case pregnancy is confirmed. All pregnant women meeting all the inclusion/exclusion criteria will be included in the study until the anticipated sample size in each selected cluster is reached.

Study 2:

Household lists of farmers participating in the 1AF programme will be used to determine whether a household has at least one eligible child between 6-35 months of age. A child will be included once inclusion and exclusion criteria have been checked and written informed consent is obtained from the caregiver. The baseline assessment will then be conducted. 1AF field officers will be responsible for recruiting the selected children.

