Life stage appropriate nutrition and WASH trainings (to participating women in intervention group in study 1 and caregivers in intervention group in study 2)
In study 1, CHVs will deliver monthly trainings to groups of mothers (according to their life cycle) and will additionally provide home counselling visits twice per month. In study 2, monthly training meetings (1 module per meeting) will be held by 1AF trainers. Training modules are currently being developed and may be adjusted for the study. The initial set of modules is presented in Table 9.

Table 9: Nutrition and WASH training modules that will be administered

Module No.	Life cycle	Topic of training module
1	Pregnant women	Nutrition for pregnant women – Diversity and frequency, caloric needs
2	Pregnant women	Nutrition ANC care (folic acid, iron, deworming)
3	Pregnant women	Impact of family planning on the nutritional status of a pregnant woman
4	Pregnant women	Water treatment, storage, food sanitation and hygiene
5	Newborns (0 to 6 months)	Immediate breastfeeding, colostrum and milk production
6	Newborns (0 to 6 months)	Breastfeeding efficacy skills - Common problems - Positions
7	Newborns (0 to 6 months)	Milk Supply - Biology - Extraction - Storage
8	Newborns (0 to 6 months)	Breastfeeding on demand Feeding through illness
9	Newborns (0 to 6 months)	Nutrition for the breastfeeding mother
10	Children under five	Timely introduction to complementary foods
11	Children under five	Routine health services and disease prevention - Growth Monitoring - Vitamin A - Deworming - Immunity and nutrition
12	Children under five	Food diversity in child feeding - 6 months - 7 to 9 months - 9 to 11 months - 12 to 23 months - 24 to 59 months (study 2 only)
13	Children under five	Food frequency in child feeding - 6 months - 7 to 9 months - 9 to 11 months - 12 to 23 months - 24 to 59 months (study 2 only)
14	Children under five	Responsive feeding Feeding through illness
15	Children under five	Sanitation and hygiene - Safe food handling - Handling of child faeces
16	Children under five	Malnutrition
17	Children under five	Water - Treatment, handling and storage
18	Children under five	Hand washing
19	Children under five	Micronutrient Powders

SMS reminders on antenatal care and life stage appropriate nutrition (to pregnant women in intervention group in study 1)

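### Participants are enrolled by programme staff after clusters have been randomised (stated for Study 1, implied for Study 2), and no concealment of allocation from recruiters is described, so enrolment can differ by arm

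*Protocol*

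**What the plan says.** **Timing.** Table 3 (section 7.1, Study 1) records "Randomisation of clusters (done prior to recruitment". Table 4, its Study 2 counterpart, has no such row. Section 7.2 says of both studies: "Once the clusters are determined, they will be randomly assigned to control or treatment in both studies". Section 7.1 describes the clusters from which participants are recruited as randomly assigned, in both studies.

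**Recruiters.** For Study 1, section 7.3.2 says: "During community meetings and outreach CHVs will inform and 1AF field officers will screen potential participants". Section 7.1 gives the screening to 1AF enumerators instead; either way it is done by 1AF staff. All eligible women are taken "until the anticipated sample size in each selected cluster is reached". In the intervention arm, section 7.4 says "CHVs will deliver monthly trainings to groups of mothers (according to their life cycle", with home counselling visits as well. For Study 2, section 7.3.2 uses existing household lists of 1AF farmers to find eligible children and adds: "1AF field officers will be responsible for recruiting the selected children". It does not say how children are selected.

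**Baseline.** Study 2 has its "baseline assessment prior to the actual start of intervention distribution". In Study 1 the package starts after the woman's round 1 visit, and the child is first measured at birth.

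**Blinding.** Sections 9.2 and 9.2.3 keep the main data analyst blinded. Nothing is said about recruiters or communities.

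**The concern.** Randomising clusters makes the clusters comparable. It makes the participants comparable only if the way they enter does not depend on the arm. If the arm is known while enrolment is open, staff may search harder, or families may respond more readily, where the package is on offer. The packages give a reason to: free LNS and eggs in Study 1, MNP, chickens and seeds in Study 2, and soap and chlorine in both. Controls have the agricultural programme already in place, plus the small incentive items that both arms receive.

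The protocol itself treats the likely routes as prognostic. Table 2 relates gestational age at enrolment, socio-economic status and food insecurity to linear growth, and expects earlier enrolment to help because exposure is longer. Intention-to-treat analysis keeps the arms as enrolled, so it preserves a difference made at enrolment. Covariates remove only what is measured and correctly modelled. Such a bias does not shrink as the sample grows.

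**Working it through.** **1. Can the arm influence enrolment?**

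| Question | Study 1 | Study 2 |
|---|---|---|
| Randomised before recruitment? | Stated (Table 3) | Implied (7.1, 7.2) |
| How participants are found | CHV outreach and meetings | Existing household lists |
| Who enrols | 1AF staff | 1AF field officers |
| Do those who find participants also deliver the package? | Yes, CHVs (7.4) | Not stated for field officers; 1AF trainers give the trainings |
| Choice among eligible people | All, up to the cluster target (about 10) | About 20 per cluster; method not described |
| Concealment during enrolment | None described | None described |
| First outcome measurement | Birth, after the intervention starts | Round 1, before distribution |

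**2. The plan's own detectable effects (section 7.2).** Inputs: two-sided alpha 0.05, power 0.80, design effect 1.3.

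- Completers per arm, Study 1: 1,200 × 0.95 × 0.80 × 0.95 × 0.75 / 2 = 324.9.
- Completers per arm, Study 2: 2,000 × 0.95 × 0.80 / 2 = 760.
- Standard error in SD units = √(2 × 1.3 / n): 0.0895 (Study 1) and 0.0585 (Study 2).
- Detectable effect = (1.960 + 0.842) × SE: 0.251 (stated 0.26) and 0.164 (stated 0.17).

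The stated figures are slightly conservative (power about 83% at each) and are not in dispute. They serve as the yardstick below.

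**3. Illustration of size.** The documents give no figure for selection, so these inputs are assumptions. Bias = share of one arm enrolled differently × mean difference of that share, in SDs of the outcome, which here is change in LAZ.

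- 10% × 0.5 SD = 0.05 SD; 20% × 0.5 SD = 0.10 SD.
- Over 5–20% and 0.25–1.0 SD the bias runs from 0.0125 to 0.20 SD. That is 5–77% of 0.26 and 7–118% of 0.17.
- Two-sided type I error = 1 − Φ(1.96 − bias/SE) + Φ(−1.96 − bias/SE):

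| Bias (assumed) | Share of 0.26 | Type I error, Study 1 | Share of 0.17 | Type I error, Study 2 |
|---|---|---|---|---|
| 0.05 SD | 19% | 8.6% | 29% | 13.7% |
| 0.10 SD | 38% | 20.1% | 59% | 40.1% |

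**4. What the change score does.** In Study 2 a constant difference in starting LAZ cancels in the change from round 1. Two things do not cancel: a difference in growth rate between the children enrolled, and regression to the mean if one arm enrols shorter children. In Study 1 the measurement at birth is already open to the intervention, so subtracting it is not a pre-intervention correction.

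**The case against.** Several limits on the risk are real and stand.

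- Study 1 must take every eligible woman up to the target, so staff may not choose among them. This does not control who comes forward or is found first.
- Section 7.2 sizes clusters so that they are likely to hold about 10 women or 20 children. If they hold few more, enrolment comes near to a census.
- The plan assumes 95% consent, which leaves little room for differential refusal. That is a planning assumption.
- Several likely confounders are listed independent variables (section 5), and socio-economic status, sex and age are minimum covariates (9.2.1).
- Study 2 children come from lists rather than self-presentation, so families coming forward is a Study 1 mechanism. In Study 2 the opening is the undescribed selection from the list, together with consent.

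A reader might infer three stronger things.

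- *That Study 2 is stated to randomise before recruitment.* The explicit row belongs to the Study 1 table; for Study 2 the order is an inference.
- *That recruiters know the allocation.* The protocol is silent. Section 10.2 has communities told of an equal chance of either arm, which would fit communities that do not yet know, but its timing relative to the draw is not given.
- *That the repair is free.* Study 2 fieldwork starts in February 2018, and seeds go out in March 2018 to match planting (Abstract, 7.4). The documents say nothing on the logistics of holding the allocation back.

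**Conclusion.** The concern holds as a weakness of design and description. Study 1 randomises first, enrols through people tied to the programme, and describes no concealment. Study 2 appears to do the same. Enrolment can therefore differ by arm, and neither intention-to-treat nor measured covariates fully repair that. The exposure is greater in Study 1, because CHVs both find women and deliver the package and because no child measurement precedes the intervention. In Study 2 the pre-intervention baseline removes part of a shift in level only.

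The documents do not show that enrolment did or will differ, and they support no estimate of bias. The figures in SD units show how sensitive the two comparisons would be under assumed selection; they are not a forecast. The point merits a change before recruitment because it concerns field conduct, which a later analysis plan cannot supply.

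**What to change.** **Study 2.** State the order of randomisation and recruitment, and how children are selected. Fix the eligible-child list for each cluster from the existing household lists. Approach children in random order up to the cluster target. Complete consent and round 1, and only then release the allocation to field officers and communities. Supply planners may hold it earlier. No extra participants or visits are needed, and the detectable effect is unchanged (0.164 recomputed, 0.17 stated). The small downside is a tight calendar before the March 2018 seed distribution.

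**Study 1.** Have CHVs list the pregnant women in a cluster, and enrol them in list order, before CHVs, enumerators and the community learn its arm. Report by arm the numbers listed, eligible and consenting, and gestational age at enrolment. The cost is a listing step within outreach already planned and a short delay before a cluster's arm is known. This reduces the risk without removing it: recruitment is planned over 3 months (section 7.2), and women identified later will be enrolled once products have made the arm visible. The reported counts would help show whether that mattered.

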7.2 Sample size and randomization

Study 1 and 2:

Some indicators included in study 1, such as maternal haemoglobin, child haemoglobin, and child length-for-age z score (LAZ), are measured more than once in the same study subject over time. This is also the case for haemoglobin and height-for-age z score (HAZ) in the children in study 2. For these indicators, the average change in outcomes in study subjects in the intervention group will be compared to the average change in study subjects in the control group. Other indicators in study 1, such as birth weight and length, are measured only once in each study subject. For these indicators, the average value in the intervention group will be compared to the average value in the control group.

The sample size depends on the size of the desired minimum difference between the intervention group and the control group, which can be detectable with statistical significance. This minimum

difference is expressed as the effect size, which is the difference in the value of the indicator between the two groups to be compared divided by the standard deviation of the indicator. For those outcomes measured more than once, the indicator is the change over time in study subjects. This effect size can be written as follows:

$$\frac{[\text{Mean}(LAZ_{C_x} - LAZ_{C_y})_{\text{Group1}} - \text{Mean}(LAZ_{C_x} - LAZ_{C_y})_{\text{Group2}}]}{\text{Standard deviation}(LAZ_{C_x} - LAZ_{C_y})_{\text{Group1}}}$$

Where C_x and C_y stand for the two measurements of those indicators which are measured twice.

The sample size calculations make the following assumptions: 1) a two-tailed comparison (that is, there is no *a priori* conclusion about which group is higher and which is lower), 2) statistical significance is defined as a p value less than 0.05, 3) the power of the study is at least 0.8, and 4) that the standard deviation of the indicator in both study groups is the same.

Although it is difficult to find highly comparable interventions and their effect sizes for key outcomes put forth, Table 5 below provides an overview of observed effect sizes for somewhat similar interventions and outcomes.

Table 5: Effect sizes in children for similar outcomes and interventions reported in the literature

Description of intervention	Reported outcome	Effect size (95%CI)	Reference
Maternal education on complementary feeding and provision of complementary foods	Weight gain	0.34 (0.11, 0.56)	[35]
	Linear growth	0.26 (0.08, 0.43)	
Maternal education on complementary feeding alone	Weight gain	0.30 (0.05, 0.54)	
	Linear growth	0.21 (0.01, 0.41)	
Micronutrient powders	Haemoglobin	0.98 (0.55, 1.40) 0.69 (0.07, 1.32) 0.33 (0.87, 1.53) 0.20 (-1.24, 1.64)	[36-40]
	LAZ	0.04 (-0.13, 0.22)	
	Serum retinol	1.66 (-1.60, 4.92)	
	Serum ferritin	1.78 (-0.31, 3.88)	
Lipid-based nutrient supplements (children)	Haemoglobin	0.63 (-0.48, 1.73) 0.52 (1.84, 2.88)	[41-43]
	Linear growth	0.22 (0.05, 0.39)	
	Weight gain	0.25 (0.19, 0.31)	
Lipid-based nutrient supplements (pregnancy&infancy)	Linear growth	0.28 (0.07, 0.50)	[44]
	Weight gain	0.24 (0.15, 0.33)	
Education on IYCF (programmes)	Linear growth	0.12 to 0.64	[45]
	Weight gain	-0.06 to 0.96	
Complementary foods and education on IYCF (programmes)	Linear growth	0.0 to 0.14	
	Weight gain	0.18 to 0.24	
Iron fortification (infants, pre-school and school-children)	Haemoglobin	0.55 (0.34, 0.76)	[37,46]
	Serum ferritin	0.91 (0.38, 1.44)	
Vitamin A fortification	Serum retinol	0.61 (0.39, 0.83)	

For study 1, considering field logistics (number of pregnant women that can be recruited within 3 months in a manageable area) the number of pregnant women that is estimated to be available for recruitment into the study is 1,200. The primary outcome is change in length-for-age z-score (LAZ) in the children of enrolled women between birth and the end of follow up at 24 months of age. The effect size that is detectable takes into account the design effect of cluster randomization (design effect = 1.3) which is based on the design effect found in other studies and study subject refusal and loss to follow up. For the latter, it was assumed that 95% of eligible pregnant women would consent to participation and that 80% of enrolled women would complete follow-up at delivery. Of children born to women completing follow-up, 95% would be recruited for continued follow-up, and 75% of enrolled

children would still be enrolled at final data collection at 24 months of age. Taking into account all these assumptions for the recruitment of a total of 1,200 pregnant women (600 women in the control and 600 women in the intervention group) in 120 clusters this will allow detecting an effect size of 0.26 in LAZ in children between 6-24 months of age, which is a reasonable effect size when compared to another study in which LNS was used during pregnancy and infancy (Table 5). Effect sizes for changes in haemoglobin concentration in children, one of the secondary outcomes in our study, are higher than for linear growth and thus our sample size will allow detecting changes in this indicator (Table 5).

Sample size was also calculated for birth weight. From prior studies of birth weight in less-developed countries, an average birth weight in the study population of 3,000 g, a standard deviation of 500 g, and a birth weight 85 g larger in the intervention population was assumed. Furthermore, it was assumed that the study drop out will be at 20%. A sample size of about 1,090 women is needed, or 545 per study arm which is covered with the calculation for the primary outcome with 600 women per arm.

For study 2, considering logistical challenges we estimated that a maximum of 2,000 children 6-35 months of age could be recruited. The primary outcome is change in length-for-age z-score (LAZ) between enrolment and after 2 years of follow up. The effect size that is detectable takes into account the design effect of cluster randomization (design effect = 1.3) as in study 1 and assumes that caregivers of 95% of eligible children would consent to participation and that 80% of enrolled children would complete the 2 years follow-up. Taking into account all these assumptions for the recruitment of a total of 2,000 children (1,000 children in the control and 1,000 children in the intervention group) in 100 clusters this will allow detecting an effect size of 0.17 in LAZ or HAZ in children between baseline and 2 years follow up, which is a reasonable effect size and has been shown in other studies before (Table 5). As in study 1, our sample size will allow detection of changes in haemoglobin concentration as effect sizes are higher than for linear growth (Table 5).

As these are cluster-randomized studies, no individual randomization will take place. Clusters will be created according to village size and location with the aim to create clusters that correspond with village(s) boundaries and are big enough to likely have 10 pregnant women to be recruited in study 1, and 20 children in study 2. The clusters will be comprised of villages that are geographically close to one another and separate from other clusters. Once the clusters are determined, they will be randomly assigned to control or treatment in both studies.

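### The birth-weight sample size of 545 per arm includes neither the assumed 20% dropout nor any design effect, so 600 per arm does not give 80% power for 85 g

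*Protocol*

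**What the plan says.** Section 7.2 sets common rules for the sample size calculations: "a two-tailed comparison", "statistical significance is defined as a p value less than 0.05", and "the power of the study is at least 0.8".

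For the Study 1 primary outcome, change in LAZ, it adds: "The effect size that is detectable takes into account the design effect of cluster randomization (design effect = 1.3"). It also allows for 95% consent and for 80% of enrolled women completing follow-up at delivery. The Study 2 calculation uses the same design effect.

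The birth-weight paragraph takes a mean of 3,000 g, "a standard deviation of 500 g, and a birth weight 85 g larger in the intervention population was assumed". It continues: "it was assumed that the study drop out will be at 20" per cent. It then concludes: "A sample size of about 1,090 women is needed, or 545 per study arm which is covered with the calculation for the primary outcome", the planned number being 600 per arm. No design effect is mentioned in that paragraph.

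**The concern.** The dropout assumption comes directly before the result, so a reader takes 545 per arm as an enrolment figure that already contains it. The same section says that clusters, not individuals, are randomised, and Section 9.2.2 says that precision and significance for the secondary outcomes will be adjusted for the sampling design. Clustering will therefore reduce the effective sample in the analysis, and the calculation should allow for it.

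If both allowances are missing, the protocol claims power for birth weight that the trial does not have. Birth weight is an impact indicator for Study 1 in Table 1, the only secondary outcome with its own sample size calculation, and one of the comparisons in the interim analysis of Section 9.2.3. A null result could be taken as coming from a trial with at least 80% power for 85 g.

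**Working it through.** **Inputs, all from protocol Section 7.2.** Two-sided alpha 0.05 (z = 1.960); power 0.80 (z = 0.842; sum 2.8016); difference 85 g; SD 500 g; dropout 20%; 600 women per arm. The design effect of 1.3 and the 95% consent come from the Study 1 LAZ calculation.

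**Step 1: reproduce the plan's figure.** Standardised effect d = 85/500 = 0.17.

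n per arm = 2 × 2.8016² / 0.17² = 543.2, rounded up to 544. The t-test solution is 544.1, rounded up to 545, or 1,090 in total. This matches the stated figure with no dropout and no design effect.

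**Step 2: the number needed once the omitted factors are applied (per arm).**

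| Allowance | Calculation | Needed |
|---|---|---|
| None | 544.1 | 545 |
| 20% dropout | 544.1 / 0.8 | about 680 |
| Design effect 1.3 | 544.1 × 1.3 | 708 |
| Both | 544.1 × 1.3 / 0.8 | 885 (1,770 total) |
| Both, and 95% consent | 544.1 × 1.3 / (0.8 × 0.95) | 931 |

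Every row after the first exceeds 600.

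**Step 3: what 600 per arm delivers.** Power = Φ(0.17 × √(n/2) − 1.96), and the difference detectable at 80% power = 2.8016 × 500 × √(2/n), where n is the effective number per arm.

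| Allowance | Effective n per arm | Power for 85 g | Detectable at 80% |
|---|---|---|---|
| 20% dropout | 600 × 0.8 = 480 | 0.75 | 90 g |
| and design effect 1.3 | 480 / 1.3 = 369 | 0.64 | 103 g |
| and 95% consent | 456 / 1.3 = 351 | 0.61 | 106 g |

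**Step 4: sensitivity to the design effect.** The protocol gives none for birth weight. With 20% dropout, assumed values of 1.0, 1.1, 1.2, 1.3 and 1.5 give power of 0.75, 0.71, 0.67, 0.64 and 0.58. None reaches 0.80.

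**Step 5: cross-check inside the protocol.** Study 2 is said to detect an effect size of 0.17 with 1,000 children per arm, design effect 1.3, 95% consent and 80% completion. Effective n = 1,000 × 0.95 × 0.8 / 1.3 = 584.6, and 2.8016 × √(2/584.6) = 0.164, close to the stated 0.17. Birth weight has the same effect size and the same 80% retention, yet is said to need only 545 per arm. On Study 2's inputs it would need 931.

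**The case against.** The strongest point on the other side is that 1.3 is not stated for birth weight. It belongs to the LAZ calculations, is taken from other studies, and need not carry over to an outcome measured at birth with more evaluable children per cluster: about 8 (10 × 0.8), against about 5.4 at 24 months (10 × 0.95 × 0.8 × 0.95 × 0.75). This stands: 64% is conditional on 1.3. It does not rescue the claim, because a design effect of 1.0 still gives only 75%.

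The 61% figure depends on whether the 1,200 are counted before or after consent. Section 7.1 speaks of recruiting 1,200, which suggests after. Section 7.3.3 describes a 46% non-consent and dropout rate, which equals 1 − 0.95 × 0.8 × 0.95 × 0.75, so the protocol does take consent off in the LAZ calculation. The text supports either reading.

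A one-sided test with dropout gives 428 / 0.8 = 535 per arm, near 545. But the protocol specifies a two-tailed comparison, the match is less close, and clustering is still left out.

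Covariate adjustment, which Section 9.2.2 allows, would raise power. The share of variance explained is not given. Assumed values of 10% to 20% give power of 0.79 to 0.84 with dropout alone, but 0.68 to 0.73 with design effect 1.3. The stated calculation makes no use of adjustment, so this does not support 545.

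Finally, birth weight is secondary, the 1,200 was set by field logistics, and Section 9.2.3 attaches no stopping rule to the interim comparison. All true. This limits the consequences but does not make the statement correct.

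**Conclusion.** The concern holds. The 545 per arm is the uninflated number of evaluable women for an individually randomised comparison, and the statement that 600 enrolled per arm covers it is wrong on the protocol's own inputs.

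Dropout alone, which the birth-weight paragraph itself states, brings power for 85 g to 75%. With the only design effect the protocol gives, power is about 64% and the difference detectable at 80% power is about 103 g. If non-consent is also taken off, these become 61% and 106 g. The chance of missing a true 85 g difference is then about 36% to 39%, not 20%. These figures assume an unadjusted comparison and, for the lower ones, that 1.3 applies to birth weight. The LAZ calculation and the planned number of women are unaffected.

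**What to change.** Keep 600 women per arm. In Section 7.2, remove the statement that the birth-weight requirement is covered by the primary calculation, and replace the sentence with, for example:

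*After 20% dropout and a design effect of 1.3 (assumed, as in the LAZ calculation), 600 women per arm give about 64% power for a difference of 85 g in birth weight; the difference detectable with 80% power is about 103 g.*

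It would help to add that power is 75% with dropout alone and about 58% at a design effect of 1.5, and to say whether the 1,200 are counted before or after consent. If before, the figures are 61% and 106 g.

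The cost is one corrected sentence and a less favourable stated power. There is no change to participants, conduct or analysis.

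### Study 2 takes over Study 1's design effect of 1.3 although its clusters are about twice as large, so its claimed power at an effect size of 0.17 is unsupported

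*Protocol*

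**What the plan says.** All of this is in Protocol section 7.2 unless noted.

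- The design effect of 1.3 is introduced for Study 1 and attributed to other studies. No ICC or cluster size is attached to it. For Study 2, the detectable effect "takes into account the design effect of cluster randomization (design effect = 1.3) as in study 1".
- Clusters are to be "big enough to likely have 10 pregnant women to be recruited in study 1, and 20 children in study 2". This agrees with the totals: 1,200 women in 120 clusters and 2,000 children in 100 clusters.
- The Study 2 claim is that recruiting 2,000 children "in 100 clusters this will allow detecting an effect size of 0.17 in LAZ or HAZ". The common assumptions are "a two-tailed comparison", "statistical significance is defined as a p value less than 0.05", "the power of the study is at least 0.8", and "that the standard deviation of the indicator in both study groups is the same".
- Expected losses in Study 2 are 95% consent and 80% completion; section 7.3.3 gives the combined loss as 24%. For Study 1, section 7.3.3 gives a combined loss of 46% by 24 months.

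**The concern.** With equal cluster sizes the design effect is 1 + (m − 1) × ICC, where m is the number of children per cluster. If m doubles and the ICC stays the same, the excess over 1 roughly doubles. One value of 1.3 therefore cannot be exact for both studies under a common ICC. Either the ICCs differ, or 1.3 is conservative for Study 1, or it is too small for Study 2. The protocol does not say which.

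What is at stake is how Study 2's primary result is read. The protocol calls 0.17 reasonable in the light of its Table 5, but that table also lists 0.04 (−0.13, 0.22) for LAZ with micronutrient powders and 0.0 to 0.14 for linear growth in programmes combining complementary foods with feeding education. Other rows are larger. A result near zero is possible, and it would be judged against a stated power whose clustering basis cannot be checked. The protocol also gives 2,000 as the most children that can be recruited, so the planning figure cannot be rescued by a larger sample.

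**Working it through.** **Inputs.** Two-sided alpha 0.05 and power 0.80, so 1.960 + 0.842 = 2.802. The effect is in SD units of the change, so SD = 1. Study 2 analysed per arm: 1,000 × 0.95 × 0.80 = 760. Enrolled cluster sizes: 1,200/120 = 10 and 2,000/100 = 20. Analysed cluster sizes: 10 × 0.95 × 0.80 × 0.95 × 0.75 = 5.415 and 20 × 0.95 × 0.80 = 15.2.

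**1. The plan's own figure.** Detectable d = 2.802 × √(2 × DE / n). With DE = 1.3 and n = 760, d = 0.164 (0.166 using t quantiles with 98 df). Power at 0.17 = Φ(0.17 × √(760/2.6) − 1.960) = 82.8%. The stated minimum of 0.8 is met. The printed 0.17 is either 0.164 rounded up or the value for a design effect of 1.4 (0.170); the document does not show which.

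**2. How large the design effect may be.** Power of 80% at 0.17 requires DE ≤ 0.17² × 760 / (2 × 7.849) = 1.40. This means ICC ≤ 0.399/19 = 0.021 at 20 per cluster, or ≤ 0.399/14.2 = 0.028 at 15.2.

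**3. ICC implied by 1.3 in each study.**

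- Enrolled sizes: Study 1, 0.3/9 = 0.033; Study 2, 0.3/19 = 0.016.
- Analysed sizes: Study 1, 0.3/4.415 = 0.068; Study 2, 0.3/14.2 = 0.021.

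**4. Study 1's implied ICC carried to Study 2 (760 per arm).**

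| Basis | ICC | Study 2 DE | Detectable d | Power at 0.17 |
|---|---|---|---|---|
| Enrolled in both (10, 20) | 0.033 | 1 + 19 × 0.0333 = 1.63 | 0.184 | 73.7% |
| Analysed in both (5.4, 15.2) | 0.068 | 1 + 14.2 × 0.0680 = 1.97 | 0.201 | 65.7% |
| Mixed (10, 15.2) | 0.033 | 1 + 14.2 × 0.0333 = 1.47 | 0.174 | 77.9% |

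**5. The opposite reading.** A shared ICC of 0.016 gives DE 1.30 in Study 2 and 1 + 9 × 0.0158 = 1.14 in Study 1. A shared ICC of 0.02 gives Study 2 a DE of 1.38 at 20 per cluster and 80.5% power, and Study 1 a DE of 1.18.

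**6. Sensitivity to the loss assumption.** If the 1,000 per arm have already consented, 800 per arm are analysed. Power at 0.17 is then 84.7% with DE 1.3, 75.8% with DE 1.63, and 80.0% with DE 1.47. Unequal cluster sizes would lower these figures, but the protocol gives no variation to work from.

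**The case against.** The strongest reply is that the only clustering assumption the protocol states is a design effect of 1.3, and that 0.17 at 80% power follows from it. That is correct. A reader might infer that the Study 2 calculation contains an arithmetic error; it does not.

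A reader might also infer that the plan assumes the ICC falls by half or more between the studies. The document does not force this. The 1.3 comes from other studies whose cluster sizes are not given, so nothing shows that it was calibrated to clusters of 10. It could be right for Study 2 and conservative for Study 1.

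Nor is a common ICC required. The studies are in different counties (section 7.1) and measure change over different ages. Section 11.1 notes that Study 2's wide age range may make its population more heterogeneous, and more variation within clusters would lower the ICC. The covariates planned in sections 5 and 9.2.1 could reduce variance as well, and the power figures here are unadjusted. The 66% result needs the further assumption that 1.3 refers to Study 1's completers, which no section says.

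All of this stands as a limit on the size of any shortfall. It does not supply the missing justification. If the shared ICC is about 0.02, Study 2 is adequately powered, but Study 1's 1.3 is then not its own design effect. Under a common ICC, at least one of the two figures needs correcting or explaining. A confidence interval will show what the final data exclude, but the protocol still makes a power claim that should rest on a stated basis.

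**Conclusion.** The design effect was carried from clusters of about 10 to clusters of about 20 without adjustment or reason, and Study 2's claim of at least 80% power at 0.17 is therefore unsupported. This is certain from the text.

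Whether power is actually short is not. The claim holds for a design effect up to about 1.40. It fails moderately (about 74% power, detectable effect 0.184) if an ICC of 0.033, inferred from Study 1 at enrolled size, carries over. The range of 66% to 78% reflects the choice of cluster-size basis. It rests on 760 analysed per arm, equal cluster sizes and no covariate adjustment. A reader might conclude that Study 2 is underpowered or that 0.17 is too optimistic; the document gives no ICC on which to base either conclusion.

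**What to change.** In section 7.2, state an ICC for change in LAZ with its source, for each study if they are thought to differ. Compute each design effect from that study's own cluster size, saying whether enrolled or analysed size is used. Restate Study 2's detectable effect, or its power at 0.17, over a range of ICCs. A range from 0.016 to 0.033 at 20 per cluster would run from 82.8% to about 74% power. This costs one recalculation and a few lines of text, with no additional children; the stated figure may become slightly less favourable.

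Also add baseline LAZ as a covariate in the Study 2 primary regression; it is already measured in round 1. Relative to a plain comparison of changes, and assuming equal variances at both times and an unchanged ICC, this multiplies the detectable effect by √((1 + r)/2), where r is the correlation between baseline and follow-up. The protocol gives no r. An assumed r of 0.6 gives a factor of 0.894, which takes 0.184 to about 0.164 but 0.201 only to about 0.180. The gain is therefore useful, but it does not restore 0.17 across the whole range.
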